6.3.5 Participant Interviews at T4

- ALL ITEMS ASKED AT T3 PLUS:
- Income (past year)
- Health Insurance (current)
- Self Efficacy
- Multidimensional Scale of Perceived Support (MSPS)
- Activities- Paffenbarger Activity Scale (PPAQ)
- Brief Pain Inventory (BPI)
- Patient Health Questionnaire Dépression Scale (PHQ-9)
- Post Traumatic Stress Disorder using the PCL Checklist

6.3.4 Retention

Every effort will be made to retain participants in the study. The study participants will receive an honorarium in recognition of their time and effort. We will provide them with challenge coin designed specifically for the METRC and (for those not on active duty), a total of \$300 to cover the costs of travel to and from the centers for the physical therapy and follow-up assessments and keep in contact with them throughout the one-year follow-up (by mail and phone). This sum will be distributed as follows: \$50 at baseline (T0), \$75 at T1, \$75 at T2 and \$100 at T4. We will also keep participants engaged through use of study updates on the METRC webpage and distribution of follow-up reminders and trinkets imprinted with the study logo.

6.3.5 Final Study Visit

Participants will complete the study at month 12. Any ongoing SAE's will be followed to resolution. The study will cover the travel expenses for participants that have moved out of the area so that they can participate in the 12 month follow up visit. Expenses that will be covered include: transportation to and from the study center (airfare, bus fare or mileage reimbursement), lodging expense (up to 1 night, if needed), meal per diem of 50.00 per day (2 day maximum).

6.3.6 Early Termination Visit

Should a participant terminate the study prematurely, if at all possible, all procedures required at the month 12 (T4) visit will be performed at his/her final visit.

6.4 Study Endpoints

	Less Demanding Tests	More Demanding Tests
Agility	4 Square Step Test	Illinois Agility Test
Strength/Power	Sit to Stand (5x)	Timed Stair Ascent (12 steps)
Speed	Self Selected Walking Speed (15 ft)	10 Meter Shuttle Run
Postural Stability	Single Leg Stance	

6.4.1 Primary Endpoints

The primary endpoints are functional performance and self reported functioning as measured using the Short Form Musculoskeletal Assessment (SMFA) and the Veterans Health Survey (VR-12).

Functional Performance The performance test battery includes a dyad of a “less demanding” test and a “more demanding” test for three of the domains. At the study initiation visit, the treating surgeon will clinically evaluate the participant’s health, weight bearing and ambulatory status and will provide written approval in order to proceed with the performance tests. Prior to and during the performance tests, the participant will be reminded that he/she can stop these activities at any point if he/she feels unsafe. Participants in the study will complete the “less demanding” test first and, if the score meets a critical threshold, they will move on to complete the “more demanding” test. This approach will provide information on higher level functioning without risking the safety of those with significant impairment. These dyads are summarized in the table below.

Details of each of these assessments are provided below.

- The Four Square Step Test (FSST)** is a dynamic test of balance and agility. It requires participants to rapidly change direction while stepping forward, backward, and sideways, over a low obstacle⁵⁴. The test has demonstrated reliability and validity through correlation with existing balance tests and a positive predictive value of 86%⁵⁴. The FSST does not require any special equipment and requires little space, and is timed using a stopwatch. Raters place four canes (or piping) in a cross on the floor (all four canes lay flat on the floor). The participant then steps as fast as possible into each square in a designated sequence (see Figure 3).
- The Illinois Agility Test**⁵⁴ is a commonly used test to measure agility by requiring the patient to turn in different directions and at different angles. The test requires the patient to

[figure not shown]

Figure 3: the Four Square Step Test

navigate through a series of cones placed 3.3 meters apart as quickly as possible. It is simple test to administer and requires little equipment. The test is timed using a stopwatch and requires 10 meters of length, 5 meters of width, and 8 cones (or markers of some kind).

- **The 5x Sit to Stand Test (STS5)**⁵⁴⁻⁶¹ is a commonly performed to assess lower extremity strength, endurance, and mobility. This test measures time to complete 5 full stands from a sitting position. It is simple, inexpensive, rapid, and reproducible, has demonstrated a highly significant relationship with age and has correlated well with measures of knee flexor and extensor muscle strength⁶¹. Participants sit in a straight back chair 44.5 cm high and 38 cm deep and are asked to fold their arms across their chests and to stand up from a sitting position once. If they successfully rise, they are asked to stand up and sit down 5 times as quickly as possible. Time to stand is measured using a stopwatch. Raw scores can be transformed into a rate per minute to accurately assess change in those who were unable to perform the test at any point.
- **Timed Stair Ascent:** The timed stair ascent is an objective measure of mobility and power⁶² that requires the patient to demonstrate greater strength and range of motion than level ground walking. Patients are asked to climb a flight of stairs at their maximal rate, with or without holding onto the railing. The rater uses a stopwatch to time the patient's ascent up 12 stairs of normal rise and run. The inclusion of this test provides data on higher levels of functional performance because of the level of challenge involved in climbing stairs
- **Self-selected walking velocity over level terrain (SSWV-L)** is a commonly used measure of speed and general physical capacity.⁶²⁻⁶⁴ Subjects will be asked to walk 30 feet on a level surface, as fast as they can, with or without an assistive device. Use of assistive devices will be recorded, as described above. The time it takes for subjects to complete the task is measured with a stop watch and recorded as feet per second (ft/sec). Use of a stopwatch has been found to have excellent concurrent validity with the gold standard of infrared timing gates, with an inter-rater reliability of 0.99 for tests of walking speed⁶⁴. Four feet per second is considered an appropriate cut-off for impaired speed, since 4.2 ft/sec is an approximate gait velocity for adults, 20-59 years old⁶³.
- **10 Meter Shuttle Run (40D):** The 10 meter shuttle run assesses speed. Research staff will measure out a continuous 10 meter stretch that is free of obstacles. This test requires the person to run or walk back and forth between two parallel lines as fast as possible. Patients will start in a standing position and run or walk at their self-selected maximal rate 10 meters and back, for a total of 20 meters. The rater uses a stopwatch to keep time. The Shuttle Run test is easy to administer and requires little equipment and space. Patients are able to run or walk at their own pace, and the test is appropriate for patients at both lower and higher levels of functional ability.
- **Single Leg Stance:** The single leg stance is a measure of postural stability⁶⁶. Participants will be asked to stand with arms crossed and pick one foot off the ground bending the knee to 90 degrees. The rater uses a stopwatch to time how long participants hold this stance up to 60 seconds. This test is done on both legs.

Self -Reported Measures of Function will be assessed at baseline (T0) and at one-year (T4).

Overall Function and Well Being will be measured using two instruments. The Short Musculoskeletal Function Assessment (SMFA) will be used to measure overall function and well being⁶⁷⁻⁶⁸. The SMFA is a shorter version of the 101-item Musculoskeletal Function Assessment (MFA) questionnaire. The SMFA is a 46-item questionnaire consisting of the dysfunction and bother index. The Dysfunction Index includes 34 items for assessing patient function. Subscores for the following 4 domains can be calculated: Daily Activities; Arm and Hand Function; Mobility and Emotional Status. The Bother Index consists of 12 items designed to detect how much patients are bothered by functional items. The SMFA has been evaluated for reliability, validity and responsiveness in patient populations⁶⁷. This scale has been chosen because it is a short, reliable, patient reported assessment of functional status that has been specifically designed for and validated in patients with musculoskeletal conditions, including acute injury⁶⁷⁻⁶⁸.

We will also use the Veterans RAND 12 item Health Survey (VR-12) as a generic health status measure from which a VR-6D can be computed for a cost-utility analysis⁶⁹⁻⁷⁰. The VR-12 is a multipurpose short-form generic measure of health status. It was developed to be a much shorter, yet valid, alternative to the VR-36 for use in large surveys of general and veteran populations. The 12 items in the VR-12 are a subset of those in the VR-36 and includes 1-2 items from each of eight health concepts: physical functioning, role limitations due to physical health problems, bodily pain, general health, vitality (energy/fatigue), social functioning, role limitations due to emotional problems and mental health (psychological distress and psychological well being).

6.4.2 Secondary Endpoints

Secondary Outcomes include additional self reported measures of participation, pain, depression and post traumatic stress. We will also be the use and satisfaction with the IDEO and related services.

- **Labor Force Participation and Work Productivity** will be assessed using standard questions used in other METRC studies. Participants will be asked what they were doing most of the time during the previous two weeks. If participants are working, the Work Productivity and Activity Impairment (WPAI) questionnaire will be administered. The WPAI measures work time missed and work and activity impairment because of a specified health problem during the past 7 days (for questionnaire: http://www.reillyassociates.net/WPAI_SHP.html)⁷¹. The validity of the WPAI has been established in a number of diseases⁷²⁻⁷³. In addition, the WPAI has proven a useful tool when measuring the relative difference between treatment groups in clinical trials and in subjects with and without disease.
- **Participation in Sports and Leisure Activities** will be assessed using the Paffenbarger Activity Scale (PAS)⁷⁴. At T0 (baseline) and at T4 (one year post fitting of the IDEO), patients are asked to identify up to 5 activities performed within the past 3 months. The 2000 version of the *Compendium of Physical Activities*⁷⁵ will be used to classify each activity according to its intensity level based on the rate of energy expenditure expressed as

metabolic equivalents (METS). Activities will then be classified as light (< 3 METS) moderate (3-6 METS) or vigorous (> 6 METS).

- **Pain** will be measured using the Brief Pain Inventory (BPI). The BPI is a widely used, 15-item measure of pain intensity and interference with daily life ⁷⁶. The questionnaire assesses three key pain domains: pain intensity, pain interference, and efficacy of pain treatments or medications. It has been extensively validated in both English and Spanish. Overall study limb as well as knee and ankle specific pain intensity will be measured using the 0-10 visual analogue scale used in the Brief Pain Inventory. Pain intensity will be measured both at rest and during ambulation. The BPI pain intensity domain is compatible with the IMMPACT guidelines for assessing pain in clinical trials and the FDA Guidance for Industry on the use of Patient-Reported Outcome Measures ⁷⁷. At each clinical follow up, the treating surgeon will also record the type (grouped as acetaminophen, opioids, GABA analogues (like Neurontin or Lyrica), and NSAIDs (like Ibuprofen or Naproxen), and other) and frequency of pain medication use.
- **Depressive Symptoms** will be assessed using the nine item depression scale of the Patient Health Questionnaire (PHQ-9) ⁷⁸. The PHQ-9 is a well validated tool for assisting clinicians in diagnosing depression. There are two components of the PHQ-9: (1) assessing symptoms and functional impairment to make a tentative depression diagnosis, and (2) deriving a severity score. The PHQ-9 is based directly on the diagnostic criteria for major depressive disorder in the Diagnostic and Statistical Manual Fourth Edition (DSM-IV).
- **Post Traumatic Stress (PTSD)** will be measured using the standard PTSD Checklist (PCL), a 17-item measure that elicits responses for each of the DSM-IV disorders that comprise the diagnostic criteria for PTSD (intrusive, avoidant, and arousal symptoms) ⁷⁹. The psychometric properties of the PCL have been well established and it is the most widely used measure of PTSD. Both civilian and military versions are available.
- **Use and Satisfaction with the IDEO and Related Services.** At T2 (following completion of the physical therapy program), and at T3 and T4, each patient will complete a brief battery of questions to assess their use and overall satisfaction with the IDEO™ and related services. We will include both the Orthotics and Prosthetics Users' Survey (OPUS) ⁸¹⁻⁸² and elements of a survey developed at the Center for the Intrepid (designed specifically for comparing the satisfaction of the IDEO with other braces) ²². The OPUS was developed by Heinemann et al. using well established contemporary measurement technology for instrument development. The OPUS consists of an 11-item measure for satisfaction with *devices* and a 10-item measure for satisfaction with *services*. Items pertaining to device satisfaction include: weight, comfort, pain associated with use, ease of use, cosmesis, durability, fit and effect of the device on clothing (i.e., dimensions). Items used to measure satisfaction with services, include wait time, respect, communication, consumer's input, team approach, and training with the device. Lastly, participants will be asked if they ever considered amputation of their injured limb, if so, why, and if they now favor limb salvage or amputation.

6.4.3 Exploratory Endpoints

N/A

6.4.4 Substudy Endpoints

N/A

7. STUDY TREATMENTS

The PRIORITI intervention consists of two components: (1) custom fitting of the IDEO; and (2) the Return to Run physical therapy program designed specifically for recipients of the IDEO. Each is described below together with specifics regarding the training of Study Site staff to ensure fidelity of the intervention across sites.

All braces will be fabricated by trained Certified Prosthetist/Orthotists (CPOs) at each participating MTF. Training for fabrication of the IDEO is described below. The two participating study MTF sites will each identify 1-2 physical therapy assistants and 1 CPO and 1 O&P tech who will provide the services necessary for measuring, fabricating and fitting the IDEO and providing the PT. Only PTAs and orthotists who have been trained for the study (see below) will be allowed to provide services to PRIORITI participants.

7.1 Fabrication and Fitting of the IDEO. The IDEO design for this study will be the modular version, since it has the advantage of modifying alignment in a simpler manner, adjusting strut stiffness for limitations or gains of individuals, and limiting fabrication responses needed for fissuring or fracturing of components of the device with use. The IDEO is constructed primarily of laminated, reinforced carbon fiber to withstand high impact forces and cyclical loading. The main components of the IDEO are the proximal cuff, strut, and foot plate. These components are described in further detail in Appendix J. The IDEO is a class 1 exempt device. A provisional patent was filed in April, 2011 by [name], CPO in conjunction with the United States Government, as represented by the Secretary of the Army (Application Serial No. 61/518,801).

The team at the Center for the Intrepid (CFI) will train the CPOs from the other two military treatment facilities in IDEO fabrication. Training will consist of a 6-8 week internship working with the San Antonio team to learn the processes of measurement, fabrication, and fitting of the brace. Training materials will be developed through this process and used in subsequent training sessions. Once able to replicate the process, the CPOs will return to WRNNMC and NMCS D to implement the program at their institutions

7.2 Physical Therapy Protocol. As indicated above, participants enrolled in PRIORITI will participate in the Return to Run physical therapy regimen. During Phase 1 (pre-IDEO) participants will engage in a home physical therapy program as prescribed by the study team for 2-4 weeks. During Phase 2 (post-IDEO), participants will receive 3 sessions of PT a week for an additional 4 weeks. Participants will be encouraged to test the IDEO under load in real world

conditions and report their experience to the study team. Each PT session will last for approximately 90 minutes. During phase 2, participants will be encouraged to complete home exercises to complement the therapy they are receiving in the clinic.

To help ensure standardization of the PT protocol across centers, several procedures will be put in place. *First*, the PTAs providing the pre-IDEO and post-IDEO physical therapy must have some documented training in sports medicine and experience working with limb trauma patients. They will be trained in the PT protocol at a 3-day training at the Center for the Intrepid in San Antonio. The 3 days will be devoted to the PT protocol with ample use made of demonstrations and practice sessions. As mentioned above, training videos will be produced and provided to the PTs or PTAs for reference. *Second*, the PTAs will be required to document the therapy provided at each session. This documentation will be reviewed on an ongoing basis by the investigators to assure the fidelity of the intervention. *Third*, the PTAs will participate in bi-weekly video conference calls together with [name] at which time individual cases will be reviewed and difficulties in providing the PT and keeping patients engaged in the program will be discussed.

8. ASSESSMENT OF SAFETY

The study will monitor and report adverse events to ensure patient safety. Definitions and procedures for reporting adverse events are designed to satisfy 45 CFR Part 46, Subpart A; the “Common Rule”, shared by 17 Departments and Agencies as well as 21 CFR 312, the FDA regulation for adverse events. The Common Rule requires written procedures and policies for ensuring reporting of “unanticipated problems” involving risks to participants to IRBs, appropriate institutional officials, and the Department or Agency Head.

The medical monitor (MM) is responsible for providing medical guidance and overseeing patient safety for the study. The MM participates in determining the course of action necessary to meet safety goals and objectives. This is achieved through the review of Serious Adverse Event reports; resolving safety issues; and interacting with Principal Investigators.

Each participating site is responsible for ensuring that all local IRB requirements for reporting adverse events (both internal and external) are met.

8.1 Definitions

8.1.1 Adverse event

Any untoward or unfavorable medical occurrence in a human subject, including abnormal sign (e.g., abnormal physical exam or laboratory finding), symptom or disease temporally associated with the subject’s participation in the study, whether or not considered related to the subject’s participation.

8.1.2 Unanticipated problem

Any incident, experience, or outcome that meets all of the following criteria:

(1) is unexpected, in terms of nature, severity, or frequency, given the research procedures that are described in the protocol and informed consent document and the characteristics of the patients eligible for the study.

(2) is related or possibly related to treatment/procedures under study; possibly related means there is a reasonable possibility that the incident, experience, or outcome may have been caused by the study procedures or treatments.

(3) suggests that the participation in the study may place subjects or others at a greater risk of harm (including physical, psychological, economic, or social harm) than was previously known or recognized.

Please note that not all adverse events are unanticipated problems and only some unanticipated problems are in fact adverse events. For instance, if a laptop containing study data is stolen, this is an unanticipated problem but it is not an adverse event since it is not an untoward or unfavorable medical occurrence in a human subject

8.1.3 Serious Adverse Event

A serious adverse event is defined as:

1. Death
2. Unanticipated events related to rigor of participating in the Return to Run PT Program; or events related to IDEO brace fit or wear.
3. Other events that are unexpected AND serious AND related or possibly related to the study

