8.2.2 AE/SAE Grading and Relationship Assignment

Adverse event grading: Adverse events will be graded using standard criteria. The study physician will determine relationship of event to the study procedure.

GRADE 1 (Mild) Transient or mild discomfort (< 48 hours); no medical intervention/therapy required

GRADE 2 (Moderate) Mild to moderate limitation in activity - some assistance may be needed; no or minimal medical intervention/therapy required

GRADE 3 (Severe) Marked limitation in activity, some assistance usually required; medical intervention/therapy required, hospitalizations possible

GRADE 4 (Life-threatening) Extreme limitation in activity, significant assistance required; significant medical intervention/therapy required, hospitalization or hospice care probable.

Relationship Assignment The relationship of the adverse event to participation in the study will be assessed as either:

Definitely related
Probably related
Possibly related
Unlikely related
Unrelated

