8.3.2 SAE and Unanticipated Problem Reporting Requirements

All Serious Adverse Events that are Unexpected AND related or possibly related to the study must be reported to the Medical Monitor and METRC Coordinating Center within 72 hours of being made aware of the event.

In addition, Unanticipated Problems (UPs) that are not adverse events must also be reported to the METRC Coordinating Center within 14 calendar days after the event has been discovered.

SAEs/UPs will be reported to the METRC Coordinating Center by entering the SAE/UP form into REDCAP. REDCap is programmed to automatically send an email to the Coordinating Center for both SAEs and Ups, and to the Medical Monitor in the case of an SAE.

The Medical Monitor for this study is:

[name], FACS
Department of Orthopedic Surgery
[name]
[name]
[contact]
[contact]
E-mail: [contact]

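### The SAE definition in Section 8.1.3 is circular and mixes seriousness with expectedness and relatedness, so SAE counts, follow-up and Medical Monitor alerts can be wrong in both directions

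*Combined protocol and SAP*

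**What the plan says.** Section 8.1.3 opens with "A serious adverse event is defined as" and lists three items:

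1. Death, without conditions.
2. A clause on therapy and the brace, worded "Unanticipated events related to rigor of participating in the Return to Run PT Program; or events related to IDEO brace fit or wear". It states no severity threshold.
3. A remainder clause for everything else, worded "Other events that are unexpected AND serious AND related or possibly related to the study".

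Section 8.2.2 grades severity from 1 to 4. Grade 1 is "Transient or mild discomfort (< 48 hours); no medical intervention/therapy required". The top grade begins "GRADE 4 (Life-threatening) Extreme limitation in activity, significant assistance required" and includes "hospitalization or hospice care probable". The same section has a five-level relatedness rating. No grade is linked to SAE status.

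Section 8.3.2 sets the 72-hour duty to the Medical Monitor and Coordinating Center: "All Serious Adverse Events that are Unexpected AND related or possibly related to the study must be reported". It also says that reporting is by entering a form in REDCap, which then emails the Medical Monitor if the event is an SAE.

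Section 8.3.4 gives the Department of Defense reporting rule twice. Numbered point 3 covers related SAEs with no expectedness condition. The closing paragraph limits the duty to events that are also unexpected.

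Under Sections 6.3.5 (Final Study Visit) and 8.5, SAEs are followed until they resolve. Section 9.2.1 has the Medical Monitor review any SAEs, all deaths, and unanticipated problems that involve risk.

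**The concern.** Seriousness, expectedness and relatedness are three separate properties of an event. Section 8.1.3 combines them and gives no criteria for the first. Two sites could classify the same event differently, and one site following the text exactly could call a trivial event serious and a grave one not.

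SAE status decides who is followed to resolution, what prompts the email to the Medical Monitor and what the Monitor reviews. Little stands behind it. Section 9.2.1 says a DSMB is not required, although the Protocol Summary and Section 1 describe one, and Sections 8.7 and 8.8 give no halting or stopping rules. What is at stake is safety oversight and the meaning of the reported SAE tally. The efficacy analysis is not affected.

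**Working it through.** No arithmetic applies: the point depends on no rate, sample size or error level. The check is to classify types of event under the written text.

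**Two readings of item 2.** Read literally, 'unanticipated' governs only the physical therapy (PT) clause, and "events related to IDEO brace fit or wear" stands without conditions. On the alternative reading the word carries across the semicolon. Both are shown. 'Unanticipated' and 'unexpected' are treated as equivalent.

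| Event | SAE under 8.1.3? | Under the 72-hour duty in 8.3.2? |
|---|---|---|
| Grade 1 brace-fit discomfort, unexpected | Yes, on both readings | Yes |
| Grade 1 brace-fit discomfort, expected | Yes literally; no on the alternative | No |
| Grade 4 event from brace wear, expected | Yes literally; on the alternative, no | No |
| Hospitalised or Grade 4, non-fatal, related, expected, not tied to the brace | No: item 2 needs unanticipated, item 3 needs unexpected | No |
| Grade 4, non-fatal, unrelated | No: item 3 needs at least possible relatedness | No |
| Non-fatal, unexpected, related, outside PT and brace | Cannot be decided: 'serious' has no criteria | Cannot be decided |
| Death | Always | Only if unexpected and at least possibly related |

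**A concrete omitted case.** Take a fall with hospitalisation during the baseline (T0) performance tests. Section 4 places these tests before the leg is cast for the brace and before either phase of PT, so neither part of item 2 can apply. Section 6.4.1 foresees a safety risk in the tests: it orders them from less to more demanding and lets participants stop if they feel unsafe. If the site therefore calls the fall expected, item 3 fails too and the event is not an SAE.

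**How the definition meets the reporting rules.**
- For item 3, the filter in 8.3.2 repeats conditions already in the definition.
- For items 1 and 2 it narrows. An expected or unrelated death is an SAE outside the 72-hour duty, although Section 9.2.1 has the Monitor review all deaths.
- The broader rule in 8.3.4 (point 3) cannot reach an expected, related, non-fatal event outside brace fit or wear, because 8.1.3 never makes that event an SAE.

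**Result.** The definition over-includes (Grade 1 brace events), under-includes (unrelated events, and expected events not tied to the brace), and leaves one class undetermined.

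**The case against.** The strongest reply is that the safety data are not lost. Adverse events are defined and recorded whatever their relatedness (Sections 8.1.1 and 8.2.1), and they are graded and rated for relatedness (8.2.2). The Monitor may reclassify events (8.2.3), and local reporting rules apply separately (8.3.1). A low threshold for brace events may also be deliberate in a study of a device labelled investigational. No endpoint, interim analysis or stopping rule uses an SAE count.

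Much of this stands, and it limits the point. It does not remove it. A later recount by grade cannot restore an alert that was not sent or follow-up that was not done. Reclassification comes after review of reports and has no stated criteria, so an event never reported as an SAE may not reach it. Section 8.3.1 also lets a site report some events locally without sending them to the Coordinating Center. A deliberate low threshold for brace events would still leave item 3 circular.

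Three stronger readings are tempting, and the documents do not support them:

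- *All expected serious events are left out.* On the literal reading of item 2, an expected serious event related to brace fit or wear is an SAE. A fall at T2 or T4 attributed to the brace would therefore qualify.
- *Every minor brace event falls under the 72-hour duty.* Section 8.3.2 has its own filter, which excludes expected ones. The REDCap email follows entry of an SAE form, and the text does not say how far sites enter forms beyond that duty.
- *SAE counts will be wrong.* No event rates are given, so the documents show only that they can be.

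**Conclusion.** The point holds as stated: Section 8.1.3 can misclassify in both directions, and one class of events cannot be classified at all. The clearest contrast uses the protocol's own scale. An unexpected Grade 1 brace-fit event is an SAE on either reading, while an unrelated non-fatal Grade 4 event is not, nor is an expected one that is not tied to the brace. The effect passes to the SAE tally, follow-up to resolution, the REDCap email and the Monitor's SAE review.

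The size in events cannot be stated. The conclusion rests on the visible protocol text. The manual of operations, the consortium policies and the draft case report forms are not shown and might define 'serious'. Section 8 says its definitions are meant to satisfy federal rules, but those rules are not in the documents and nothing here relies on them. The text should be corrected because safety oversight depends on it.

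**What to change.** - In 8.1.3, define seriousness by outcome alone, using categories the protocol already names: death, life-threatening, hospitalisation.
- Keep the relatedness rating in 8.2.2 and add a separate expectedness field to the case report form.
- Keep brace-fit and PT-rigor events as a list that is always recorded, and flag them as SAEs only when they meet the seriousness criterion.
- Reconcile 8.3.2 and the two versions of the rule in 8.3.4 with the new definition, and state which SAEs go to the Medical Monitor. Rewriting 8.1.3 alone would leave expected serious events outside the 72-hour duty.

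The cost is text changes in three sections and a change to the case report form. The SAE tally will then include some expected or unrelated hospitalisations. The relatedness and expectedness fields allow these to be shown separately.
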